9.1.9 BMI

BMI equals a person's weight in kilograms divided by height in meters squared ($BMI = \text{kg}/\text{m}^2$).

BMI will be rounded to the nearest whole number according to the standard convention of 0.1 to 0.4 round down and 0.5 to 0.9 round up.

9.1.10 12-Lead ECG

Special care must be taken for proper lead placement by qualified personnel. Skin should be clean and dry before lead placement. Subjects may need to be shaved to ensure proper lead placement. Female subjects may need to remove their bras.

Subjects should be resting in a semirecumbent position for at least 5 minutes before each ECG measurement.

QT intervals with Fridericia correction method (QTcF) will be used to calculate QT intervals in this trial.

A predose ECG will be obtained within approximately 30 minutes before dosing. This measurement will be used as the baseline. The principal investigator should arrange to have a trial cardiologist available as needed to review ECG tracings with abnormalities.

If a subject demonstrates an increase in QTcF interval ≥ 40 msec compared with a predose baseline measurement, the ECG will be repeated within 5 minutes. The average value of the QTcF interval from the 2 ECGs will represent the value at that time point. If the average QTcF interval increase from Baseline for any postdose time point is ≥ 40 msec, the subject will continue to be monitored by repeat 12-lead ECGs every 60 minutes for at least 4 hours or until the QTcF is within 40 msec of the baseline value. If prolongation of the QTcF interval ≥ 40 msec persists, a consultation with a trial cardiologist may be appropriate and the sponsor should be notified.

If the QTcF interval is ≥ 500 msec, the sponsor should be notified and the ECGs should be reviewed by a cardiologist. The subject should be telemetry-monitored (until the QTcF is <500 msec) or should be considered for transfer to a location where closer monitoring is available.

If the subject has unstable hemodynamics, or has any clinically significant dysrhythmias noted on telemetry, the subject should be immediately transferred to an acute care setting for definitive therapy.

If repeat ECGs are required, the clinical site will decide whether to leave the electrodes in place or mark the position of the electrodes for subsequent ECGs. To mark the position of the electrodes, 12-lead electrode sites will be marked on the skin of each subject with an ECG skin marker pen to ensure reproducible electrode placement.

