7.11.3 Vital Signs

Descriptive statistics (N, mean, SD, median, minimum, and maximum) will be used to summarize vital sign parameters at baseline, each post-baseline visit, and change from baseline to each post-baseline visit. No inferential statistics will be presented.

For each vital sign parameter, boxplots for predose/ postdose values and the change from the predose by hepatic function group will be prepared.

Individual results of vital signs that meet Takeda's markedly abnormal criteria (see [Appendix A](#)) will be summarized and provided in the data listings. If a subject has a MAV for a particular vital sign parameter, all visits for that subject for that parameter will be listed. The number and percentage of subjects with at least 1 postdose MAV signs measurement will be summarized by hepatic function group. The mapping of the subjects who meet the MAV criteria will be listed as a table. All observations, including ones at unscheduled visits, will be included in the MAV evaluation and summaries.

All vital sign results for all subjects in the Safety Set will be listed by subject in the data listings and markedly abnormal values will be flagged.

7.11.4 12-Lead ECGs

The scheduled 12-lead ECG data will be collected according to [Appendix C](#). The ECG parameters include heart rate, PR-interval, QRS-duration, QT-interval, QTcF interval, and the interpretation of the ECG profile by the principal investigator.

Descriptive statistics (N, mean, SD, median, minimum, and maximum) of ECG parameters will be presented for baseline, each post-baseline visit, and changes from Baseline in quantitative ECG parameters to each post-baseline visit. Only the scheduled measurements will be included in the summary. If more than 1 ECG parameter is measured at the same scheduled time point, the latest value will be used. No inferential statistics will be presented.

Individual results of quantitative ECG parameters from the 12-lead safety ECGs that meet Takeda's markedly abnormal criteria (see [Appendix B](#)) will be provided in the data listings. Shift tables will be generated to show the investigator's ECG interpretations at each postdose collection by the interpretation at Baseline.

All ECG data will be presented in the listings. ECG MAVs will be flagged in the listings.

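### ECG markedly abnormal values are listed but not counted by hepatic group, and the scheduled-only summary can miss QTcF peaks on triggered hourly repeats

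*SAP*

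**What the plan says.** **Vital signs (SAP 7.11.3).** MAVs are tabulated: "The number and percentage of subjects with at least 1 postdose MAV signs measurement will be summarized by hepatic function group". Unscheduled data count: "All observations, including ones at unscheduled visits, will be included in the MAV evaluation and summaries".

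**ECGs (SAP 7.11.4).** Descriptive statistics are planned for baseline, each post-baseline visit and the change between them, with this limit: "Only the scheduled measurements will be included in the summary". Quantitative results that meet the Appendix B criteria "will be provided in the data listings. Shift tables will be generated to show the investigator's ECG interpretations at each postdose collection". The section ends: "All ECG data will be presented in the listings. ECG MAVs will be flagged in the listings". It plans no number or percentage of subjects with an ECG MAV.

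**Triggered ECGs (Protocol 9.1.10).** A QTcF rise of at least 40 msec from the predose baseline leads to a repeat within 5 minutes. If the average of the two still shows such a rise, "the subject will continue to be monitored by repeat 12-lead ECGs every 60 minutes for at least 4 hours", or until QTcF is back within 40 msec of baseline. A separate rule applies at 500 msec.

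**Schedule (Protocol 3.0, SAP Appendix C).** Postdose ECGs are due at 1, 2 and 4 h on Day 1, at 24, 48 and 72 h, and at Follow-up.

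**Protocol 11.1.4.4** promises descriptive ECG summaries, shift tables of the investigator's interpretation, and listings.

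**The concern.** Safety across degrees of hepatic function is the secondary objective. QTcF is an ECG measure that the protocol actively manages, through exclusion criterion 5, the 40 msec rule and the 500 msec rule. Yet two adjacent SAP sections treat abnormal values differently and give no reason. A reader of the tables can see how many subjects per hepatic group had a markedly abnormal blood pressure, but not how many had a markedly abnormal QTcF.

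The scheduled-only limit adds to this. The tracings taken because QTcF was prolonged are mostly unscheduled, so the most informative QTcF values are those most likely to be missing from the tabulated extremes. A comparison of QTcF outliers between groups would then depend on someone counting flags in a listing.

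**Working it through.** The plan states no figure to reproduce on this point. The check enumerates the triggered ECGs and then works one example through the Appendix B rule.

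**Step 1: which hourly repeats fall on a scheduled time.** Inputs: the seven scheduled postdose ECGs in SAP Appendix C, and four hourly repeats per trigger from the 4-hour period in Protocol 9.1.10. Assumption: the trigger occurs at a scheduled ECG.

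| Trigger | Hourly repeats | On a scheduled time | Off schedule |
|---|---|---|---|
| 1 h | 2, 3, 4, 5 h | 2 h and 4 h | 2 |
| 2 h | 3, 4, 5, 6 h | 4 h | 3 |
| 4 h | 5, 6, 7, 8 h | none | 4 |
| 24 h | 25 to 28 h | none | 4 |
| 48 h | 49 to 52 h | none | 4 |
| 72 h | 73 to 76 h | none | 4 |
| Follow-up | +1 to +4 h | none | 4 |

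Total: 7 × 4 = 28 repeats. On schedule: 2 + 1 = 3. Off schedule: 28 − 3 = 25. This counts possible times and is not a probability, because triggers need not be equally likely at each time. Where two tracings share a scheduled time, the SAP says: "If more than 1 ECG parameter is measured at the same scheduled time point, the latest value will be used".

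**Step 2: effect on the tabulated extremes (assumed values).** Baseline QTcF is 400 msec. At 4 h it is 440 msec, with the same value on the 5-minute repeat. On the hourly ECG at 6 h it is 460 msec. All other scheduled values are lower than at 4 h.

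- Change at 4 h (scheduled): 440 − 400 = +40 msec.
- Change at 6 h (unscheduled): 460 − 400 = +60 msec.
- The tabulated maximum change is +40, so it is understated by 60 − 40 = 20 msec.

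**Step 3: does a MAV count catch this subject?** Appendix B defines a high QTcF MAV as at least 500 msec, or a change of at least 30 msec together with a value of at least 450 msec.

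- 4 h: 440 is below 450, so it is not a MAV. 6 h: the change is 60 and the value 460, so it is a MAV.
- A count on scheduled ECGs gives 0/8. A count on all observations gives 1/8 = 12.5%.

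The result depends on baseline. A +60 msec peak reaches 450 only if baseline is at least 450 − 60 = 390 msec. A +40 msec value reaches 450 only if baseline is at least 450 − 40 = 410 msec. So for this pattern:

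| Baseline (msec) | Scheduled-only count | All-observations count |
|---|---|---|
| below 390 | 0 | 0 |
| 390 to below 410 | 0 | 1 |
| 410 or more | 1 | 1 |

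The maximum change is understated by 20 msec in all three rows. A subject with a baseline of 380 msec would be monitored hourly, peak at 440 msec and never be a MAV. A MAV count alone can therefore miss triggered subjects, whereas a table of per-subject maxima would not.

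**The case against.** The strongest reply is that nothing is lost and nothing promised is missing. All ECGs are listed, MAVs are flagged, and nothing exempts unscheduled tracings from flagging, so a count can be recovered later. Protocol 11.1.4.4 asks for summaries, shift tables and listings, and the SAP plans all three. Laboratory summaries in SAP 7.11.2 are also scheduled-only. This stands, and it limits the point to an improvement.

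A reader might go further and infer that the triggered ECGs enter no table at all. The documents do not support that:

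- Three of the 28 repeats fall on scheduled times.
- The shift tables cover each postdose collection with no stated scheduled-only limit, so inclusion there is unclear. They show the investigator's interpretation and not msec, so they would not close the gap.
- A change judged clinically significant can be recorded as an AE (Protocol 10.1) and so reach the TEAE tables. Repeat noninvasive testing does not count as an intervention under that section, so the hourly ECGs alone do not create an AE.

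A reader might also treat the 20 h between the 4 h and 24 h ECGs as excluded data. It is only a gap in the schedule. Hourly tracings would fill it only if prolongation persisted.

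Nor can a compound-specific QT concern be inferred. Background text is redacted, and the amendment rationale describes the QTcF exclusion as a standard criterion.

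For heart rate the objection largely succeeds. Vital-sign heart rate is due at every scheduled ECG time and also at 0.5 h, 12 h and Day 5. It is counted by group against the same limits (below 50, above 120 bpm).

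**Conclusion.** The point holds for QTcF. The SAP plans no by-group count of ECG MAVs, although it plans one for vital signs. Its quantitative ECG summary leaves out 25 of the 28 minimum triggered repeats, and all of them after a trigger at 4 h or later. The tabulated maximum QTcF and maximum change can therefore be lower than values that occurred, by 20 msec in the assumed example.

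The 25 of 28 assumes triggers at scheduled ECGs and four repeats each. If monitoring stops sooner because QTcF recovers, there are fewer repeats, but those after a 4 h or later trigger are still all off schedule. The 1/8 result holds only for the assumed changes with a baseline from 390 to below 410 msec.

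The primary PK analysis is untouched. With 8 subjects per group any count is descriptive: 1/8 has an exact 95% interval of 0.3% to 52.7%. The change is worth making because it is cheap and serves the secondary objective.

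**What to change.** In SAP 7.11.4:

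1. Tabulate n (%) of subjects with at least one postdose QTcF MAV by hepatic function group, using the Appendix B criteria as finalised and all postdose observations, including unscheduled ones. This is the rule already written in 7.11.3.
2. Tabulate each subject's maximum postdose QTcF and maximum change from baseline by group, again from all observations.
3. Keep the by-time-point summaries on scheduled ECGs.
4. State whether the shift tables include unscheduled tracings.
5. Add a footnote that subjects with triggered repeats have more tracings and so more chances to be counted or to show a higher maximum.

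An ECG heart-rate MAV count is optional.

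One related inconsistency should be settled at the same time. For two ECGs at one time point, Protocol 9.1.10 takes the average QTcF and SAP 7.11.4 takes the latest value. These passages must be reconciled, because the choice affects any table of maxima.

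The cost is SAP wording and one or two tables from data already collected, with the vital-sign MAV program reusable. No procedure, threshold or monitoring rule changes.

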7.11.5 Other Observations Related to Safety

Physical examination findings will be presented in the data listings.

7.12 Interim Analysis

Not applicable.

7.13 Changes in the Statistical Analysis Plan

**8.0 BASED ON CONSULTATION WITH PHARMACOVIGILANCE, THE
CORRECTED CALCIUM WILL BE SUMMARIZED, RATHER THAN
CALCIUM AS STATED IN THE PROTOCOL. REFERENCES**

1. A Phase 1, Nonrandomized, Open-Label Trial to Evaluate the Effect of Hepatic Impairment on the Single Dose Pharmacokinetics of Intravenous TAK-954, Takeda Development Center Americas, Inc. and Takeda Development Centre Europe Ltd., Amendment 01, Trial No. TAK-954-1006, dated 06 October, 2017.

Appendix A Criteria for Abnormal Changes from Baseline of Vital Signs

Parameter	Unit	Lower Criteria	Upper Criteria
Heart Rate	bpm	<50	>120
Systolic blood pressure	mm Hg	<85	>180
Diastolic blood pressure	mm Hg	<50	>110
Body temperature	°C	<35.6	>37.7

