The additional vital sign measurements added are aligned with PK measurements taken at same timepoints and will add to the evaluation of any potential tachycardia or hypotension.

Change 14: Added exclusion criteria for restricted concomitant medications.

The primary change occurs in Section 7.2 Exclusion Criteria.

Description Added the following exclusion criteria for Groups 1 through 3: **Are unable to refrain** of change: **from or anticipates the use of:**

- **strong CYP3A4 inhibitors or inducers**
- **serotonin agonists or antagonists**
- **monoamine oxidase inhibitors**
- **noradrenergic agonists**
- **selective serotonin reuptake inhibitors**
- **gamma—aminobutyric acid antagonists**
- **N-methyl-D-aspartate receptor antagonists**

beginning approximately 7 days before administration of the trial drug,

throughout the trial, until the Follow-up Visit.

Rationale for Change:

Restricted concomitant medications (in Section [7.3 Excluded Medications, Supplements, and Dietary Products](#) and others added to minimize the risk of serotonin syndrome) were inadvertently omitted from exclusion criteria in the original protocol.

Section [7.3 Excluded Medications, Supplements, and Dietary Products](#) also contains this change.

Amendment 1 to A Phase 1, Non-Randomized, Open-Label Trial to Evaluate the Effect of Hepatic Impairment on the Single Dose Pharmacokinetics of Intravenous TAK-954

ELECTRONIC SIGNATURES

Signed by	Meaning of Signature	Server Date (dd-MMM-yyyy HH:mm 'UTC')
PPD	Clinical Pharmacology Approval	09-Oct-2017 10:57 UTC
	Statistical Approval	09-Oct-2017 13:47 UTC
	Pharmacovigilance Approval	09-Oct-2017 14:23 UTC
	Clinical Science Approval	09-Oct-2017 19:11 UTC

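### The count of subjects with a postdose vital-sign abnormality does not separate new abnormalities from those present at baseline, and the heading of SAP Appendix A does not match its content

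*SAP*

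**What the plan says.** SAP Appendix A carries the heading "Criteria for Abnormal Changes from Baseline of Vital Signs". Its four rows are:

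- "Heart Rate bpm <50 >120"
- "Systolic blood pressure mm Hg <85 >180"
- "Diastolic blood pressure mm Hg <50 >110"
- "Body temperature °C <35.6 >37.7"

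No row has a change term. SAP 7.11.3 refers to the same table under another name: "Individual results of vital signs that meet Takeda's markedly abnormal criteria". It then sets the counting rule: "The number and percentage of subjects with at least 1 postdose MAV signs measurement will be summarized by hepatic function group". Readings from unscheduled visits are included. Nothing in the rule refers to the baseline value, although SAP 7.1 defines baseline as the last predose observation.

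SAP 7.11.3 also provides descriptive statistics of change from baseline at each visit, boxplots of change from predose by hepatic function group, a listing of all vital signs, and a listing of every visit for any subject and parameter with a MAV.

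**The concern.** There are two separate matters.

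**Heading against content.** The heading announces criteria for change; the table holds limits on the value itself. A programmer cannot tell from the appendix whether the heading is wrong or columns are missing.

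**Counting rule.** A postdose count by group will be read as what happened after the drug. As written, it mixes abnormalities that began after dosing with abnormalities that were already there and persisted or came back. The groups may differ at baseline. Under Protocol 7.3, hepatically impaired subjects may keep their concomitant medication while healthy subjects may not. Inclusion criterion 9 makes healthy subjects similar in age, weight, gender and race, not in heart rate or blood pressure. Safety across degrees of hepatic function is the trial's secondary objective, and this is the only vital-sign summary that classifies individual subjects against a threshold.

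**Working it through.** The documents give no figure to reproduce. The check applies the Appendix A limits and the 7.11.3 rule directly, then uses an illustration to size the effect of the fix.

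**1. What the rule counts.** A subject counts if any postdose value is outside a limit.

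| Predose → postdose | Change | Counted now | Counted if baseline must be within limits |
|---|---|---|---|
| HR 48 → 48 | 0 | yes | no |
| SBP 84 → 84 | 0 | yes | no |
| HR 52 → 49 | −3 | yes | yes |
| HR 60 → 118 | +58 | no | no |
| SBP 178 → 86 | −92 | no | no |

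A subject with a predose HR of 48 and every postdose reading at 50 or above (none over 120) is not counted under either rule.

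**2. Weight of one subject.** 1/8 = 12.5 percentage points in a group of 8.

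**3. Largest change that no limit catches** (upper limit minus lower limit): HR 120 − 50 = 70 bpm; SBP 180 − 85 = 95 mm Hg; DBP 110 − 50 = 60 mm Hg; temperature 37.7 − 35.6 = 2.1 °C.

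**4. Number of chances to be counted.** SAP Appendix C schedules postdose HR and blood pressure at 0.5, 1, 2, 4 and 12 hours, on Days 2, 3, 4 and 5, and at Follow-up: 5 + 4 + 1 = 10 readings.

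**5. How much the baseline-restricted line removes.** These inputs are assumptions and are in neither document: no drug effect; a subject's usual DBP T ~ N(μ, 8²); one baseline and 10 postdose readings, independent given T, each N(T, 5²). With p(T) = Φ((50 − T)/5):

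- all subjects: E[1 − (1 − p)^10]
- baseline not below 50: E[(1 − p)(1 − (1 − p)^10)]

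| Group mean μ | All subjects | Baseline not below 50 | Share removed | Expected count of 8, before → after |
|---|---|---|---|---|
| 78 | 0.9% | 0.8% | 10% | 0.07 → 0.06 |
| 70 | 7.5% | 6.1% | 18% | 0.60 → 0.49 |
| 65 | 19.5% | 14.7% | 25% | 1.56 → 1.17 |
| 60 | 39.2% | 25.8% | 34% | 3.14 → 2.07 |

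Comparing a group at mean 65 with one at mean 78, the difference in expected counts goes from 1.56 − 0.07 = 1.49 to 1.17 − 0.06 = 1.11. About 1.11/1.49 = 74% of a difference that owes nothing to the drug remains.

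**6. Why so much remains.** Most of it is repeated reading near a limit. Take a usual HR of 52 and an assumed within-subject SD of 3 bpm. The chance that one whole-number reading is below 50 is Φ((49.5 − 52)/3) = 0.202, and the chance of at least one in 10 is 1 − 0.798^10 = 0.90. Such a subject will often have a baseline inside the limits.

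**The case against.** The strongest reply is that the heading is a slip and the rest is already covered. Much of this stands.

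- **A reader might infer that change limits were planned and then lost.** The documents do not support that. SAP 7.11.3 calls the table markedly abnormal criteria, Appendix B has a parallel heading to that effect with the same heart-rate limits, and Appendix B writes out a change from baseline for QTcF where one is wanted. A mislabelled heading is the likelier explanation.
- **A reader might infer that any abnormal baseline becomes a postdose event.** It does not. A postdose reading must also be outside the limit. In the illustration, between 38% (mean 78) and 7% (mean 60) of subjects with a baseline DBP below 50 are never counted.
- **A reader might infer that large falls or rises go unseen.** They are not flagged as MAVs, but they appear in the minimum and maximum of change at each visit, the boxplots and the listings. Protocol Appendix E says the extra readings "will add to the evaluation of any potential tachycardia or hypotension". That explains why readings were added; it does not promise a change threshold.
- **No figure in the documents shows that impaired subjects start lower.** The means and SDs above are assumed, and inclusion criterion 10 requires every subject to be judged healthy or medically stable, partly on vital signs.

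What the reply does not answer is the count itself. The all-visits listing lets a reader work out by hand who was abnormal at baseline, but the by-group table does not show it.

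**Conclusion.** The point holds, at minor severity. The Appendix A heading and content disagree, and the postdose MAV count in 7.11.3 cannot distinguish a new abnormality from one that persists or recurs from baseline. Both follow from the SAP text and need no assumption. In a group of 8, each such subject is worth 12.5 percentage points.

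The benefit of the added line does rest on assumed DBP means and SDs: about a quarter of the no-effect count at mean 65 and a third at mean 60. It makes the table easier to interpret, but it does not remove group differences that arise from a usual level close to a limit. The case for new change-from-baseline cut-offs is not made. The table is descriptive, with no inferential statistics, and none of the primary PK endpoints depends on it.

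**What to change.** 1. In SAP 7.11.3, report the postdose MAV count by hepatic function group and parameter on two lines: all subjects, and subjects whose baseline value (as defined in SAP 7.1) was not a MAV for that parameter. Show the denominator for each line. Add a note that the second line reduces, but does not remove, differences due to a usual level near a limit.
2. Reconcile the Appendix A heading with its content, and state whether a change criterion was intended. If it was not, retitle the appendix as criteria for markedly abnormal vital signs.

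No change cut-offs need to be added. The cost is a wording change in the SAP and one extra line per parameter in a table already planned. The HR and blood-pressure data needed, including the predose readings, are already scheduled.

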Appendix B Criteria for Identification of Markedly Abnormal 12-Lead ECG Parameters

Parameter	Unit	Lower Criteria	Upper Criteria
HR	bpm	<50	>120
QTcF-interval	msec	≤50	≥500 OR ≥30 change from baseline and ≥450

